## **Pregnancy Rates**

The percentage of subjects with positive  $\beta$ hCG, clinical pregnancy, vital pregnancy, and ongoing pregnancy will be described for each of the two protocols and for subgroups based on age strata and AMH. Pregnancy rates will be compared between the long GnRH agonist protocol and the GnRH antagonist protocol using a logistic regression model with treatment (long GnRH agonist or GnRH antagonist), age stratum ( $<35$ , 35-37, or 38-40 years), and AMH at screening ( $<15$  pmol/L or  $\geq 15$  pmol/L) as factors. The results of this analysis (in terms of odds for pregnancy) will be converted into proportions, differences in proportions, and 95% CIs for differences in proportions using the delta method.

To account for subjects withdrawing from the trial before starting FE 999049 treatment, the multiple imputation method applied for the primary endpoint will be used, using a logistic regression model instead of a negative binomial regression model. Pregnancy data for subjects with pregnancies occurring before start of FE 999049 treatment will not be included in the analysis. These subjects are withdrawn and their data will be imputed.

Missing pregnancy assessments will be assumed to indicate a negative test. If, however, a subsequent test is positive, a previous missing assessment will be considered as positive (if e.g. the clinical pregnancy assessment is missing but the ongoing pregnancy assessment is positive, the missing clinical pregnancy assessment will be regarded as positive).

The main analyses of pregnancy rates will be based on subjects in the FAS, but excluding subjects that had transfer cancellation due to the COVID-19 pandemic. Additional analyses will be made for the FAS, and also for subjects in the FAS that started treatment with FE 999049, i.e. without using multiple imputations (i.e. the safety analysis set).

### **Implantation Rates**

The implantation rate will be calculated as the number of gestational sacs 5-6 weeks after transfer divided by the number of blastocysts transferred.

Ongoing implantation rate will be calculated as the number of intrauterine viable fetuses 10-11 weeks after transfer divided by the number of blastocysts transferred.

The implantation rate and the ongoing implantation rate will be described for each of the two protocols and for subgroups based on age strata and AMH at screening.

## **11 Safety**

### **11.1 OHSS**

#### **Proportion of Subjects with Early OHSS (including OHSS of Moderate/Severe grade)**

Incidence of early OHSS will be tabulated by classification (mild, moderate, severe, moderate or severe) and grade (1, 2, 3, 4, 5). Early OHSS is defined as OHSS with onset  $\leq 9$  days after triggering of final follicular maturation. Note this includes OHSS with onset before triggering and OHSS with onset during stimulation where triggering is not performed.

#### **Proportion of Subjects with Late OHSS (including OHSS of Moderate/Severe grade)**

Incidence of late OHSS will be tabulated by classification (mild, moderate, severe, moderate and severe) and grade (1, 2, 3, 4, 5). Late OHSS is defined as OHSS with onset  $> 9$  days after triggering of final follicular maturation.

**Proportion of Subjects with Any OHSS (including OHSS of Moderate/Severe grade)** Incidence of any OHSS will be tabulated by classification (mild, moderate, severe, moderate and severe) and grade (1, 2, 3, 4, 5).

## 11.2 Adverse Events

Adverse events will be coded using MedDRA. The version of MedDRA will be documented. Adverse events will be grouped according to start of FE 999049 as follows:

- Pre-treatment adverse event, i.e. any adverse event occurring after signed informed consent and before start of FE 999049 treatment, or a pre-existing medical condition that worsens in intensity after signed informed consent but before start of FE 999049 treatment.
- Treatment-emergent adverse event, i.e. any adverse event occurring after start of FE 999049 treatment and before the end-of-trial visit, or a pre-treatment adverse event or pre-existing medical condition that worsens in intensity after start of FE 999049 treatment and before the end-of-trial visit.

Treatment-emergent adverse events will be presented in summary tables and listings. Pre-treatment adverse events will be presented in a listing only. Treatment-emergent adverse events will be summarised overall and tabulated by System Organ Class (SOC) and PT in decreasing order of frequency. The total number of subjects reporting an adverse event, the percentage of subjects with an adverse event, and the number of events reported will be presented.

Summary tables will be produced for the following: all adverse events, adverse events by causality (reasonable possibility / no reasonable possibility), adverse events leading to death, adverse events by intensity (mild / moderate / severe), adverse reactions by intensity (mild / moderate / severe), serious adverse events, adverse events leading to discontinuation, adverse events with an incidence of  $\geq 5\%$  in any treatment group, and non-serious adverse events with an incidence of  $\geq 5\%$  in any treatment group.

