## **6.11 Clinical Pregnancy**

Subjects with a positive  $\beta$ hCG test must attend a visit 5-6 weeks after transfer.

The following must take place:

- Transvaginal ultrasound of uterus to assess any clinical pregnancy
- Recording of use of any concomitant medication
- Recording of adverse events

If at least one gestational sac (either intrauterine or ectopic) is observed, this confirms a clinical pregnancy. If at least one intrauterine gestational sac with fetal heart beat is observed, this confirms a vital pregnancy. For subjects with a vital pregnancy, the next visit is the ongoing pregnancy visit (section 6.12). Subjects with no vital pregnancy must undergo end-of-trial assessments (section 6.13).

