### **7.2.19 Adverse Events**

Adverse events will be recorded from the signed informed consent for participation in the trial until the end-of-trial visit. For each adverse event the following parameters are recorded by the investigator on the Adverse Event Log: description of event, date and time of onset, intensity, causal relation to IMP, action taken to IMP, other actions taken, seriousness of the adverse event, date and time of outcome, and outcome. Furthermore, the pattern (e.g. the frequency, time of onset, intensity, seriousness and outcome) of the most frequent / relevant adverse events will be tabulated.

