### **Date and Time of Onset**

The date of onset is the date when the first sign(s) or symptom(s) were first noted. If the adverse event is an abnormal clinically significant laboratory test or outcome of an examination, the onset date is the date the sample was taken or the examination was performed.

---

e Exception: if an adverse event with onset before the first IMP administration (i.e. a pre-treatment adverse event) worsens in intensity after IMP administration, this must be recorded as two separate events. The initial adverse event should be recorded with outcome “not recovered” and the date and time of outcome is when the intensity changed. The second adverse event should be recorded with date and time of onset when the intensity changed.

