### **Adverse Events**

Adverse events will be coded using MedDRA. The version of MedDRA will be documented. Adverse events will be grouped according to start of FE 999049 as follows:

- Pre-treatment adverse event, i.e. any adverse event occurring after signed informed consent and before start of FE 999049 treatment, or a pre-existing medical condition that worsens in intensity after signed informed consent but before start of FE 999049 treatment.
- Treatment-emergent adverse event, i.e. any adverse event occurring after start of FE 999049 treatment and before the end-of-trial visit, or a pre-treatment adverse event or pre-existing medical condition that worsens in intensity after start of FE 999049 treatment and before the end-of-trial visit.

Treatment-emergent adverse events will be presented in summary tables and listings. Pre-treatment adverse events will be presented in a listing only. Treatment-emergent adverse events will be summarised overall and tabulated by System Organ Class (SOC) and PT in decreasing order of frequency. The total number of subjects reporting an adverse event, the percentage of subjects with an adverse event, and the number of events reported will be presented.

Summary tables will be produced for the following: all adverse events, adverse events by causality (reasonable possibility / no reasonable possibility), adverse events leading to death, adverse events by intensity (mild / moderate / severe), adverse reactions by intensity (mild / moderate / severe), serious adverse events, adverse events leading to discontinuation, adverse events with an incidence of  $\geq 5\%$  in any treatment group, and non-serious adverse events with an incidence of  $\geq 5\%$  in any treatment group.

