### 8.2 Medical History and Concomitant Medication

Medical history and concomitant medication will be presented for the FAS. Medical history recorded at the screening visit will be coded using MedDRA and summarised. The version of MedDRA will be documented. Prior and concomitant medication will be summarised by ATC classification 1st level (alphabetically) and ATC classification 2nd level (in decreasing order of frequency). These medications will be tabulated separately for:

- Prior medication, i.e. medication taken exclusively prior to treatment (i.e. with stop date/time before date/time of 1st IMP administration)

- Concomitant medication, i.e. medication taken during the treatment period (i.e. medication that was not stopped before date/time of 1st IMP administration and not started after the end-of-trial visit)

If the timing of the dose of a concomitant medication cannot be established in relation to the administration of IMP, it will be considered as concomitant medication.

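### The treatment-emergent window closes before the end-of-trial visit, so an event with onset at that visit, such as a silent pregnancy loss first seen on the final scan, has no place in the SAP 11.2 adverse-event tables

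*SAP*

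**What the plan says.** SAP 11.2 sorts adverse events into two classes by their timing relative to FE 999049.

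- Pre-treatment: "any adverse event occurring after signed informed consent and before start of FE 999049 treatment", or worsening of an existing condition in that same interval.
- Treatment-emergent: "Treatment-emergent adverse event, i.e. any adverse event occurring after start of FE 999049 treatment and before the end-of-trial visit", or worsening within that same window.

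Protocol 9.6.3 (Adverse Events) gives the same upper limit: "any adverse event occurring after start of FE 999049 treatment and before the end-of-trial visit". Neither document has a third class.

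The classes determine the output: "Treatment-emergent adverse events will be presented in summary tables and listings. Pre-treatment adverse events will be presented in a listing only".

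Collection is described differently. Protocol 7.2.19 states: "Adverse events will be recorded from the signed informed consent for participation in the trial until the end-of-trial visit". Protocol 6.13 makes recording of adverse events a required procedure at the last scheduled visit.

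**The concern.** Collection runs to the end-of-trial visit, but classification stops just short of it. That would matter little if events rarely had their onset at that visit. The protocol, however, directs one kind of event there. Pregnancy loss is one of the two adverse events of special interest in Protocol 8.3, and in many women the visit at which a scan would reveal it is also the last scheduled visit.

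A programmer who follows the SAP literally would code a strict inequality. The tables by system organ class and preferred term would then keep losses that had announced themselves by symptoms and omit those found silently on the final scan. That is under-counting by mode of detection. The SAP plans no separate pregnancy-loss table that would pick them up.

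**Working it through.** No sample size or event count enters this point. The check is to lay the rules side by side and apply them to dated cases.

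**Step 1. When is the end-of-trial visit?** Protocol 6.13 places the end-of-trial assessments at the last scheduled visit, and footnote d of the flow chart (Table 6-1) says the same. For a woman with a vital pregnancy, 6.13 names the ongoing-pregnancy visit at 10-11 weeks. For the others, Protocol 6.11 says of the 5-6 week visit: "Subjects with no vital pregnancy must undergo end-of-trial assessments". Women with a cancelled cycle (6.6.4), no oocytes retrieved (6.7) or a negative βhCG test (6.10) also go to these assessments.

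**Step 2. How is a loss documented?** Under Protocol 8.3.2, spontaneous abortion is documented by ultrasound, ectopic pregnancy by ultrasound or surgery, and biochemical pregnancy by the absence of a sac on a later scan or by reported menstruation.

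**Step 3. What is its onset date?** Protocol 8.2.2 has two rules. If there were signs or symptoms, onset is when they were first noted. If the event is itself an abnormal test or examination result, "the onset date is the date the sample was taken or the examination was performed".

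**Step 4. Combine.** A loss with no earlier sign or symptom, first seen at the 5-6 week scan (no vital pregnancy) or the 10-11 week scan (no viable fetus), takes the date of that scan. That date is the end-of-trial visit.

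**Step 5. Apply the class definitions.** As written, pre-treatment means consent < onset < first dose, and treatment-emergent means first dose < onset < end-of-trial visit. The last column replaces the final < by ≤ and compares calendar dates.

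| Event in an exposed woman | As written, date and time | As written, date only | Upper limit inclusive, by date |
|---|---|---|---|
| (a) Bleeding 3 days before the visit | treatment-emergent | treatment-emergent | treatment-emergent |
| (b) Symptom at 07:00 on the visit day, visit at 10:00 | treatment-emergent | neither | treatment-emergent |
| (c) Scan finding at the visit | neither | neither | treatment-emergent |

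Case (c) fails under both ways of comparing. Case (b) depends on whether clock times are used. Onset time is recorded, but the required source data in Protocol 10.1 name visit dates without times.

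**Step 6. Is the loss picked up later?** After the end of the trial, Protocol 8.6.2 asks only for serious events that the investigator considers possibly caused by the product. Late losses under 8.3.2 are those after ongoing pregnancy. Neither route returns case (c) to the tables.

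**Step 7. Compare a neighbouring rule.** SAP 8.2 counts a medicine as concomitant if it was "not started after the end-of-trial visit", among other conditions. That limit includes the visit; the adverse-event limit does not.

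**The case against.** The strongest reply is that the intent is obvious. Events are recorded until the visit and must be recorded at it, and the medication rule includes it, so the strict limit is probably a drafting slip. I agree about the likely intent. But neither document says that the limit is inclusive, and the written rule is what will be programmed.

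Other parts of the reply stand and limit the point.

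- A reader might infer that these events drop out of every safety table. They do not. The OHSS tables in SAP 11.1 rest on onset relative to triggering, or on no time limit for any OHSS. They do not use treatment-emergent status.
- A reader might infer that loss rates are understated. Neither document defines a loss rate. Positive βhCG, clinical, vital and ongoing pregnancy are each described and compared by protocol, so a scan-detected loss still shows as a fall between stages. What is missing is its record as an adverse event.
- A reader might infer that pregnancy losses as a class are lost. Losses with earlier signs or symptoms keep the earlier onset and stay in, and a biochemical pregnancy shown by menstruation need not be dated by a scan.
- A reader might infer a bias between the arms. The same rule applies to both, and nothing in the documents shows a differential effect.

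It could also be said that the first table listed in SAP 11.2, covering all adverse events, would catch the missing cases. The preceding paragraph reserves summary tables for treatment-emergent events, so the natural reading is all events of that class.

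**Conclusion.** Wrong as written. In an exposed woman, an event with onset at the end-of-trial visit fits neither class and has no place in the summary tables or listings of SAP 11.2. The main case is a pregnancy loss without earlier signs or symptoms, first found at a scan visit that is also end-of-trial. The conclusion rests on the literal reading of the upper limit and on the examination-date rule for onset.

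The size cannot be computed. The count per arm would be 200 × (positive βhCG rate − ongoing pregnancy rate) × (share of losses first found at the final scan). Of these, the documents give the planned 200 per arm and, from ESTHER-1, an ongoing pregnancy rate of 30.7% with FE 999049 under an antagonist protocol. They give neither a positive βhCG rate nor the share found by scan, so any count would be the product of two guesses. The defect does not depend on the count.

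The primary analysis, the pregnancy-rate endpoints and the OHSS tables do not change.

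**What to change.** In SAP 11.2 and Protocol 9.6.3, replace *before the end-of-trial visit* by *up to and including the end-of-trial visit*. The phrase occurs twice in each definition, once for new events and once for worsening events, and both need the change. Keep the condition that onset or worsening comes after the start of FE 999049. It helps to add that the upper limit is compared by calendar date, so that clock times on the visit day do not decide the class.

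Do not add a general sentence that everything found at end-of-trial assessments is treatment-emergent. Under Protocol 6.13 those assessments also apply to women who discontinue early, including women withdrawn before any FE 999049, for example after failed down-regulation. Such a sentence would mislabel events in unexposed women and events with onset before the first dose.

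The cost is one phrase in two places in each document and one inequality in the program. SAP Section 14 states that the SAP makes no changes to the protocol's analyses, so if only the SAP is edited, the change should be recorded there.

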### 6.4 Down-regulation

Subjects randomised to controlled ovarian stimulation with FE 999049 in a long GnRH agonist protocol will start down-regulation in the mid-luteal phase (i.e. cycle day 21-24) of their menstrual cycle.

The following must take place at the down-regulation visit prior to GnRH agonist administration:

- Check withdrawal criteria and ensure that the subject is still eligible for participation in the trial
- Urinary pregnancy test – must be negative

Once the above has been done, the subject will start down-regulation with GnRH agonist:

- Dispensing and administration of GnRH agonist [the first administration of GnRH agonist takes place at the clinic and can be done by either delegated trial staff or the subject under supervision by the delegated trial staff]

Finally, this must be done before the subject leaves the clinic:

- In the first 30 min following the GnRH agonist administration, the delegated trial staff must observe the subject's general health with emphasis on symptoms of an acute allergic reaction
- Instruct the subject to administer the GnRH agonist at a daily dose of 0.1 mg throughout the stimulation period
- Recording of use of any concomitant medication
- Recording of adverse events
- Hand out the diary to the subject. The subject must be instructed to record administration of GnRH agonist

A new visit must be scheduled for confirmation of down-regulation after 14 days ( $\pm 1$  day) of GnRH agonist treatment.

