## 6.6 Stimulation

### 6.6.1 Stimulation Day 1

Subjects randomised to controlled ovarian stimulation with FE 999049 in a long GnRH agonist protocol will attend the stimulation day 1 visit after down-regulation is confirmed (*note: this can be on the same day as the visit for confirmation of down-regulation or within 2 days after down-regulation is confirmed*).

Subjects randomised to controlled ovarian stimulation with FE 999049 in a GnRH antagonist protocol will attend the stimulation day 1 visit on day 2-3 of the menstrual cycle.

The following must take place before administration of the first dose of FE 999049:

- Check withdrawal criteria and ensure that the subject is still eligible for participation in the trial
- Body measurements (body weight) [once the body weight has been entered into the e-CRF, the FE 999049 dose will be calculated and displayed within the system]
- Pregnancy test – must be negative
- Transvaginal ultrasound of uterus and ovaries (endometrial thickness, ovarian volume, number and size of follicles). If a cyst  $\geq 10$  mm is observed (functional or not), it should be punctured before treatment is initiated.b If the cyst was present at the screening visit, it should have been recorded on the medical history form. If the cyst presented between screening and stimulation day 1, it should be recorded on the adverse event form.
- Blood collection for central laboratory analysis of endocrine parameters (treatment panel; FSH, LH, inhibin B, progesterone and estradiol, and additionally AMH)

Once the above has been completed, the following must be performed by the delegated trial staff:

- Dispense FE 999049 to the subject and instruct the subject on how to administer FE 999049

b Treatment can be initiated the same day. If puncture is not possible, stimulation may be postponed to the next menstrual cycle for subjects randomised to controlled ovarian stimulation with FE 999049 in the GnRH antagonist protocol, assuming that the cyst will disappear, that the subject fulfils the inclusion criteria and that stimulation day 1 can take place within 90 days from screening.

- Administer the 1st dose of FE 999049 according to AMH level at screening and body weight at stimulation day 1 [administration of FE 999049 takes place at the clinic and can be done by either the delegated trial staff or the subject under supervision by the delegated trial staff]

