### **6.6.2 Stimulation Day 6**

The following must take place at stimulation day 6:

- Transvaginal ultrasound of uterus and ovaries (endometrial thickness, endometrial triple-layer structure, endometrial echogenicity pattern, number and size of follicles)
- Blood collection for central laboratory analysis of endocrine parameters (treatment panel) – the blood sample must be drawn at least 8 hours after the latest administration of FE 999049 and, if applicable, prior to administration of GnRH antagonist
- Dispensing of FE 999049 as needed
- Dispensing of GnRH agonist as needed [*note*: only applicable for subjects randomised to controlled ovarian stimulation with FE 999049 in a long GnRH agonist protocol]
- Dispensing and administration of GnRH antagonist [*note*: only applicable for subjects randomised to controlled ovarian stimulation with FE 999049 in a GnRH antagonist protocol; the first administration of GnRH antagonist takes place at the clinic and can be done by either the delegated trial staff or the subject under supervision by the delegated trial staff]
- Drug accountability of FE 999049 and, if applicable, GnRH agonist
- Recording of use of any concomitant medication

- Recording of adverse events
- The subjects randomised to controlled ovarian stimulation with FE 999049 in a GnRH antagonist protocol must be instructed to record administration of GnRH antagonist

Finally, this must be done before the subject leaves the clinic [*note*: only applicable to subjects randomised to controlled ovarian stimulation with FE 999049 in a GnRH antagonist protocol]:

- In the first 30 min following the GnRH antagonist administration, the trial medication delegate (or another qualified trial staff) must observe the subject's general health with emphasis on symptoms of an acute allergic reaction.
- Instruct the subject to administer the GnRH antagonist at a daily dose of 0.25 mg throughout the stimulation period.

After the stimulation day 6 visit, the next visits must be scheduled at least every second day throughout the remaining stimulation period. When the leading follicle reaches  $\geq 15$  mm, visits must be performed daily.

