#### Secondary Objectives

- To evaluate the effect of individualised FE 999049 treatment on other pharmacodynamic parameters in a long GnRH agonist protocol versus a GnRH antagonist protocol
- To evaluate the effect of individualised FE 999049 treatment on pregnancy rates in a long GnRH agonist protocol versus a GnRH antagonist protocol
- To evaluate the safety of individualised FE 999049 treatment in a long GnRH agonist protocol versus a GnRH antagonist protocol

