#### 4 Trial design

This is a randomised, controlled, open label, parallel group, multicentre trial comparing the efficacy and safety of individualised FE 999049 dosing in first cycle patients aged 18-40 years undergoing controlled ovarian stimulation for IVF/ICSI following either a long GnRH agonist protocol or a GnRH antagonist protocol. The trial has been designed to describe potential differences in the mean number of oocytes retrieved with adequate precision.

Subjects will be screened within 90 days prior to randomisation for compliance with the inclusion and exclusion criteria. Randomisation may take place as soon as all eligibility criteria are met. Subjects will be randomised in a 1:1 ratio to controlled ovarian stimulation with FE 999049 in a long GnRH agonist protocol or to controlled ovarian stimulation with FE 999049 in a GnRH antagonist protocol. Randomisation will be stratified by centre and according to age (<35, 35-37 and 38-40 years). The subject will be informed of treatment allocation and when to start treatment by the delegated trial staff.

Subjects randomised to treatment with FE 999049 in the long GnRH agonist protocol will start down-regulation with GnRH agonist (triptorelin acetate, GONAPEPTYL) 0.1 mg/day subcutaneously in the mid-luteal phase (i.e. cycle day 21-24) of their menstrual cycle. Ovarian stimulation with FE 999049 will start after 14 days ( $\pm 1$  day) if the subject has experienced withdrawal bleeding and down-regulation criteria are fulfilled. If down-regulation is confirmed and ovarian stimulation is initiated, treatment with GnRH agonist is continued throughout the stimulation period. If the subject has not experienced withdrawal bleeding after 14 days ( $\pm 1$  day), a urinary pregnancy test is to be performed. If the subject is not pregnant and down-regulation is not confirmed, treatment with GnRH agonist will be continued and stimulation will be postponed until down-regulation is confirmed. Subsequent visit(s) for confirmation of down-regulation will be scheduled according to local practice. If down-regulation is not achieved after 28 days, treatment with GnRH agonist will be stopped and the subject will be withdrawn from the trial.

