### 7.2 Safety Analysis Set

The safety analysis set will consist of all subjects that were randomised in the trial and were exposed to FE 999049. In all presentation of safety data subjects will be presented according to the protocol they were actually treated with.

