Subjects in the FAS that did not start treatment with FE 999049 will not have any data after exposure to FE 999049. For these subjects, post-randomisation data will only be imputed for the purpose of statistical analysis, using multiple imputation techniques. In tables, figures and listings all post-randomisation data from these subjects will be missing. Therefore tables, figures and listings will be based on subjects in the FAS starting treatment with FE 999049, i.e. randomised and exposed subjects (i.e. same as the safety analysis set).

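### Adverse events that begin during down-regulation, when only the agonist arm is on a trial drug, stay out of the by-arm tables unless they worsen later

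*SAP*

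**What the plan says.** The safety objective in SAP 3.1 is comparative: "To evaluate the safety of individualised FE 999049 treatment in a long GnRH agonist protocol versus a GnRH antagonist protocol".

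SAP 11.2 calls an adverse event pre-treatment if it occurs between consent and the first FE 999049 dose. It calls the event treatment-emergent if it starts, or worsens in intensity, after that dose. Every planned summary table is of treatment-emergent events. For the rest, "Pre-treatment adverse events will be presented in a listing only". Protocol 9.6.3 has the same rule.

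SAP 7.2 (and Protocol 9.4.2) restricts the safety population: "The safety analysis set will consist of all subjects that were randomised in the trial and were exposed to FE 999049". Safety data are presented by the protocol each woman was actually treated with.

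SAP 4 gives the timelines. The agonist arm takes daily triptorelin first: "Ovarian stimulation with FE 999049 will start after 14 days" (± 1 day) if the down-regulation criteria are met. Otherwise triptorelin continues, and a woman not down-regulated after 28 days is withdrawn. In the antagonist arm FE 999049 is itself the first trial drug, and the antagonist follows on stimulation day 6.

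SAP 10.1, in the efficacy chapter, adds: "Therefore tables, figures and listings will be based on subjects in the FAS starting treatment with FE 999049".

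**The concern.** Starting the count at the first dose of the investigational product is a sound convention for profiling FE 999049 alone. Here the randomised comparison is between two protocols, and down-regulation is part of one of them. The cut-off removes time on a trial drug from the agonist arm and none from the antagonist arm, so the by-arm tables understate the burden of the agonist protocol. In a descriptive trial these tables are the safety comparison.

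There is a second gap. A woman given triptorelin and withdrawn before FE 999049 is outside the safety set. The tables of serious events and of events leading to discontinuation therefore cannot contain an event that ended down-regulation. The efficacy analysis treats the same women differently: apart from COVID-19 discontinuations, it keeps them in the FAS and imputes their outcomes.

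**Working it through.** No figure in the plan is at stake, so the check traces the definitions and then sizes the exposure that they leave out.

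**The same kind of event under the rules**

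| Event | Where it goes |
|---|---|
| Acute allergic reaction to the first agonist dose (Protocol 6.4: "In the first 30 min following the GnRH agonist administration, the delegated trial staff must observe") | Pre-treatment, listing only |
| Acute allergic reaction to the first antagonist dose (Protocol 6.6.2: "In the first 30 min following the GnRH antagonist administration, the trial medication delegate (or another qualified trial staff) must observe") | Treatment-emergent, tabulated by arm |
| New cyst before stimulation day 1 (Protocol 6.6.1: "If the cyst presented between screening and stimulation day 1, it should be recorded on the adverse event form") | Pre-treatment, listing only; Protocol 1.3 names cysts as a known complication of the agonist |
| Any event in a woman withdrawn during down-regulation | In no adverse event table; listing unclear because of SAP 10.1 |

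Two routes lead into the tables for an event first seen in down-regulation. It may worsen after FE 999049 starts (SAP 11.2). Or it may resolve and recur after that point, in which case the recurrence is a separate record (Protocol 8.2.2). The first episode stays untabulated.

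**Inputs (SAP 4 and 4.2)**
- Down-regulation: 13 to 15 days when the criteria are met at the first check, and at most 28 days. Protocol 6.5 allows stimulation day 1 up to 2 days after confirmation, so 28 does not overstate the longest case.
- Stimulation: at most 20 days, with the agonist continued throughout.
- About 200 women per arm.

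**Share of agonist days before tabulation begins** = down-regulation days / (down-regulation days + stimulation days)
- 13/(13+20) = 39.4%
- 14/(14+20) = 41.2%
- 28/(28+20) = 58.3%

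Shorter stimulation raises the share, so 39% is a lower bound for women who start FE 999049. If stimulation lasts 8 to 12 days (an assumption; the documents give no typical length), 14 days of down-regulation gives 14/26 = 54% to 14/22 = 64%. For a woman withdrawn in down-regulation the share is 100%. For the antagonist it is 0%.

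**Woman-days outside the tables**, if about 200 women reach the day-14 check: 200 × 13 = 2,600, up to 200 × 28 = 5,600 if every woman needed 28 days. The antagonist arm has 0 trial-drug days outside the tables.

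**Scale in women:** 1% of 200 = 2 women. The tables of events with at least 5% incidence begin at 5% × 200 = 10 women.

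**Illustration on assumed rates (not in the documents).** Let 40% of each arm have a treatment-emergent event. Let a fraction p of the agonist arm have, independently, a down-regulation event that neither worsens nor recurs. The planned tables show a difference of 0. Counting the down-regulation events, the agonist rate is 1 − 0.60 × (1 − p):
- p = 5% (10 women): 43%, a difference of 3 points
- p = 10% (20 women): 46%, a difference of 6 points
- p = 20% (40 women): 52%, a difference of 12 points

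The 95% CI half-width at p = 5% is 1.96 × √(0.43 × 0.57/200 + 0.40 × 0.60/200) = 9.7 points, and it is about the same for the other two.

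**The case against.** The objective can be read as the safety of FE 999049 within each protocol. FE 999049 is the only investigational product, triptorelin is a non-investigational one, and causality is rated against the investigational product only. Protocol and SAP agree on the rule, and it was fixed in advance. On that reading the cut-off is deliberate. It does justify keeping the FE 999049-emergent tables. It does not make them a comparison of two randomised protocols. And because causality is rated only for FE 999049, the all-cause tables are the only place where a triptorelin effect could show by arm.

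The cyst rule is the same in both arms, so it is not unequal in itself. That stands. The imbalance comes from the agonist being a recognised cause.

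The SAP 10.1 sentence sits in the efficacy chapter and may not be meant for adverse event listings. That is fair. The text leaves it unclear, and one sentence would settle it.

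The percentages are shares of exposure, not of missed events, and the 5,600 figure is an extreme. Both points stand.

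There is partial cover. Events are collected from consent, discontinuations are summarised by time and reason (SAP 5), agonist days are summarised (SAP 9), and reactions to the agonist go to pharmacovigilance (Protocol 8.6.4). None of these gives adverse event terms, intensity or seriousness by arm.

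**Conclusion.** The concern holds. By the SAP's own definitions, an adverse event confined to down-regulation reaches no summary table, and women given only triptorelin are outside the safety set. This affects one arm only, for 39% or more of each starter's agonist days. The 39% rests on the documents' limits of 13 days before FE 999049 and 20 days with it. The direction is clear: the agonist protocol's burden is understated. The size in women or events cannot be derived from the documents, and the 3 to 12 point illustration rests wholly on assumed rates.

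The data are collected, and neither the primary analysis nor any test is touched. The point should still be fixed, because the tables as planned do not deliver the protocol-versus-protocol safety comparison.

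**What to change.** 1. Keep the FE 999049-emergent tables as planned.
2. Add to SAP 7 a second safety set: all randomised women who received any trial medication (GnRH agonist or FE 999049).
3. For that set, tabulate by arm the adverse events by SOC and PT, serious adverse events, and adverse events leading to discontinuation. Count onset or worsening from the first dose of any trial medication, split into before and after the first FE 999049 dose.
4. State in SAP 10.1 and 11.2 that women withdrawn before FE 999049 are included in the adverse event listings.
5. Record these as added analyses in SAP 14. The reporting rule for menstrual bleeding in Protocol 8.4.1 stays as it is.

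**Cost:** SAP wording and a few tables. No new data are needed: events are recorded from consent (Protocol 7.2.19), and the date of the first agonist dose is recorded in the diary (Protocol 5.6.2).

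**Downside:** more output and less favourable agonist-arm figures. Part of any excess will reflect longer time on a trial drug, since the antagonist arm contributes no time before FE 999049 to these tables. That is why the before/after split should be shown and the two periods not only pooled.
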